8.2 Aim 2 (mixed methods mediation analysis) procedures

In depth interviews (IDIs) with trial participants will take place in a private and quiet location with the use of an interview guide. A semi-structured guide (Appendix VI) will include questions to assess the following domains: 1) Experiences related to MF groups, 2) Barriers/facilitators to accessing HIV care, including household economic conditions, food security, geography/distance, social support, and HIV-related stigma; 3) How participation in MF and/or community-based care impacts retention in care,

adherence to ART; 4) Satisfaction with HIV care delivery (community-based or facility-based); 5) Suggested improvements for care delivery models.

In depth interviews (IDIs) with intervention delivery personnel will take place in a private location, outside of their work location if preferred. Interviewers will be trained members of the AMPATH social behavioral team. Semi-strucutred interview guides (Appendix VII) with staff will focus on the following domains: 1) Satisfaction with job; 2) Challenges to delivering HIV care in the community; 3) Suggested improvements; 4) Context-specific issues delivering care in this setting related to geography, community, etc. Interviews will be conducted in Swahili or English by a trained member of the research staff and audio-recorded with permission. All interviews will be transcribed and translated in full. Transcriptions will be entered into a text organization software program for analysis.

8.3 Aim 2 statistical analyses

Quantitative mediation analyses. We will use causal mediation analysis to evaluate the importance of causal pathways between microfinance and integrated community-based care and viral suppression and retention. We will use the data described in Aim 1 collected at baseline, 9-month, and 18-month follow-up visits. The primary analysis will focus on two main mediators: household economic conditions and access to care. We will estimate the mediation effect of each mediator separately using the difference method and account for multiple comparisons using a Bonferroni correction. The generalized linear models needed to implement the difference method will adjust for key confounders such as education, location, gender, and age. We will perform a sensitivity analysis of the assumption of no unmeasured mediator-outcome confounders. As a secondary analysis, we will use causal mediation analysis to evaluate the mediation effect of food security, social support, and HIV-related stigma. We hypothesize that there will be similar improvements in household economic conditions between the two MF and MF+ICB groups, but that barriers in access to care will be more improved in the MF+ICB arm. Differences in these mechanisms will provide important information regarding the additive impact of integrated community-based care on the hypothesized relationships.

Qualitative mediation analyses. Text from the n=50 interviews will be coded into a hierarchical, branching structure in which broad concepts are first identified, along the domains identified in the interview guides and our conceptual model, and then themes and variations within those themes will be defined and text will be labeled according to these definitions. Coded data from intervention participants will be compared to identify mechanisms through which MF and community-based care impacted retention in HIV care and adherence to ART, and the additive impact of the community-based care delivery in the intervention group. Specifically, data will compare between the intervention arms the added benefits of community-based care, beyond those relevant to both groups from the MF activities. We will triangulate findings using data from the qualitative study to explain and expand on findings from the quantitative mediation analysis.

9. Aim 3. Cost-effectiveness analysis

Aim 3 will perform a cost-effectiveness analysis to test the working hypothesis that microfinance groups with integrated community-based care (MF+ICB) are more cost-effective compared to microfinance without ICB (MF+SOC) and standard care (SOC).

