- HbA1C test: A hemoglobin A1C test will be conducted among all microfinance group members in the integrated care arm during the baseline visit and during the final 18-month visit in the community if their RBS > 7.8 mmol/L or if their FBS > 6.1 mmol/L. The baseline and endline tests will be sponsored by the study.
- Systolic and diastolic blood pressure will be assessed during each clinical evaluation conducted in the community using a routine blood pressure cuff.
- (2) one-on-one referrals of the patient by the clinical officer to a health facility for emergency or acute care needs that cannot be addressed in the community (i.e., becomes virally unsuppressed/viremic, presents with new opportunistic infection, is lost to follow up, has moved out of study county, or another reason).
- (3) group-level health education during which the clinical officer will discuss positive HIV management habits, and health lifestyle habits for managing chronic conditions, and GISHE group members will be able to ask questions together.

For one-on-one activities, each participant will be invited to a private location near their group meeting location (e.g., private room in a community hall, empty classroom in an empty school) to meet with the clinical officer. For group-level health education activities, groups will convene in their regular GISHE meeting location (e.g., in an empty community hall, outdoors away from other crowds).

Clinical encounter data, medication distribution data and data on referrals will be recorded in REDCap in the community and then transferred to the patient's medical record by the clinical officer when the clinical officer returns to the facility.

- 7. Aim 1 RCT Methods: Data collection, management, and analysis
- 7.1 Data Collection

The trial involves the collection and use of the following types of data. With the exception of viral load data which will be ascertained from and/or entered directly into patient medical records, data will be collected using mobile tablets with secure encryption and cloud-based data capture.

1. We will measure HIV viral load at study enrollment and at 18-months for all enrolled trial participants.

- 1.1 Baseline viral load will reflect the most recent viral load measurement available in the patient's medical record within the 12 months prior to their enrollment date.

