- 1.2 18-month viral load will be assessed using blood draws taken during the 18-month assessment in the community (for microfinance group members) and at the facility (for non-microfinance group members).
- 2. For clinical secondary outcomes, we will measure systolic blood pressure and hemoglobin A1c at baseline and 18-months for all 900 microfinance group members enrolled in the trial. Blood pressure will be measured in the community by the clinical officer using a blood pressure arm cuff. HbA1c will be measured in the community by the clinical officers using a point of care test.
- 3. For non-clinical secondary outcomes, we will measure retention in care on an ongoing basis for all enrolled trial participants. Retention in care will be based on study records (REDCap) for intervention recipients and on medical records for facility care patients.
- 4. For exploratory outcomes and mediation analyses, we will collect survey data from all enrolled trial participants: at enrollment and 18-months for all trial participants, with an additional round of survey data collection at month 9 for all microfinance group members. Surveys will be administered by a research assistant to participants in a private location in-person. Surveys will assess demographics, health insurance enrollment and utilization, social support (Oslo Social Support Scale-3), quality of life (adapted version of the MOS-HIV scale), psychological distress (Patient Health Questionnaire-4), self-reported ART adherence (based on the adapted ACTG Adherence Questionnaire), self-reported adherence to NCD medications (based on the extent of DOSE-Nonadherence Questionnaire), barriers to accessing care, patient satisfaction with care, felt HIV stigma (9-item measure of felt stigma validated in Kenya). The survey instrument is included in Appendix III. For exploratory outcomes, we will collect data on microfinance group performance (e.g., saving and lending activities, loan default rates) for all microfinance group participants. Microfinance group performance data will be collected on a quarterly basis and recorded via REDCap. The microfinance data collection tool is included in Appendix IV.

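### The mediation models do not name the baseline mediator or baseline viral load as covariates, so part of an A versus B effect can be wrongly credited to access to care

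*Combined protocol and SAP*

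**What the plan says.** On the estimator, section 8.3 states: "We will estimate the mediation effect of each mediator separately using the difference method and account for multiple comparisons using a Bonferroni correction". On the mediators: "The primary analysis will focus on two main mediators: household economic conditions and access to care". On covariates: "The generalized linear models needed to implement the difference method will adjust for key confounders such as education, location, gender, and age". The four covariates are given as examples, so the list is open. The section adds "We will use the data described in Aim 1 collected at baseline, 9-month, and 18-month follow-up visits", without saying what part the baseline values play in the models. Its one stated safeguard is "We will perform a sensitivity analysis of the assumption of no unmeasured mediator-outcome confounders", with no method or parameters.

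Both omitted variables are to hand. Section 7.1, item 4, says "we will collect survey data from all enrolled trial participants: at enrollment and 18-months for all trial participants", and the Appendix III survey covers barriers to care and household economic status. Section 5 places randomisation of the groups after the baseline assessments. Section 7.1, item 1.1, says "Baseline viral load will reflect the most recent viral load measurement available" in the medical record. The section 7.2 model for suppression has baseline viral load as a covariate, and so do the revised dropout and outcome models in addendum item 10. The addendum does not revise the Aim 2 analysis.

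**The concern.** Randomising groups to arm A or B balances the arms. It does not make the follow-up mediator independent of other causes of suppression or retention. Someone who had trouble reaching care before the trial is likely to have trouble later, and may be less likely to be suppressed for reasons that the later trouble did not cause. If the models leave out that earlier status, the follow-up mediator stands in for it. When the intervention also moves the mediator, the arm coefficient shrinks once the mediator enters, and the difference method reports the shrinkage as mediation.

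At stake is the Aim 2 conclusion on mechanism. The exposed pathway is the one the investigators expect to find, since section 8.3 predicts that "barriers in access to care will be more improved in the MF+ICB arm". With positive confounding the error runs in favour of that prediction.

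**Working it through.** The plan gives no power, sample size or expected mediated share for Aim 2, so there is no figure to reproduce. The check is a simulation of A versus B with a true mediated effect of zero.

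**Inputs.** From the documents: the difference method, and a 15-point effect at 20% to 50% control suppression (section 3.4.2). Assumed, with no source in the documents: 85% suppression in arm B at average baseline status, a mediator shift a = 0.4 SD, a log odds ratio of 0.8 per SD of baseline status, a baseline to follow-up correlation ρ of 0.3 to 0.6, no demographic covariates and no clustering.

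**Model.** Baseline mediator M0 ~ N(0,1). Follow-up mediator M = ρ·M0 + 0.4·A + noise. Outcome: logit P(Y=1) = logit(0.85) + 0.4·A + 0.8·M0 + 0·M.

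**Estimator.** On the risk-difference scale, fit Y on A (coefficient c), then Y on A and M (coefficients c′ and b). The mediated effect is c − c′ = a·b, and the share is a·b/c. Averaged over participants, suppression is about 82.4% in B and 87.1% in A, so c is about 4.7 points.

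| ρ | b | a·b | c | Share without M0 | Share with error-free M0 |
|---|---|---|---|---|---|
| 0.3 | 0.0289 | 0.4 × 0.0289 = 0.0116 | 0.0473 | 24% | 0% |
| 0.5 | 0.0474 | 0.4 × 0.0474 = 0.0190 | 0.0473 | 40% | 0% |
| 0.6 | 0.0570 | 0.4 × 0.0570 = 0.0228 | 0.0474 | 48% | 0% |

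The true share in each row is 0%. Repeat runs differ by about 1 point, hence a range of about 23% to 48%.

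**How far it depends on the inputs** (ρ = 0.5 throughout):
- Mediator not shifted: a = 0, so a·b = 0 and the share is 0%.
- Larger total effect: at 40% control suppression and a 16-point effect, 0.4 × 0.0854 / 0.1605 = 21%. Over 20% to 50% control suppression with the planned 15 points, it is about 17% to 21%.
- Weaker confounding: at log odds ratio 0.3, 0.4 × 0.0164 / 0.0452 = 15%. With a 15-point effect as well, it is about 9%.
- Demographics carrying 30% of the variance of baseline status (assumed): 40% falls to about 31%.
- Noisy baseline score included as covariate: at reliability 0.7, 0.4 × 0.0173 / 0.0474 = 15% remains. At reliability 0.5, about 22% to 23% remains.

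**Which omitted covariate matters.** A second simulation used a stable trait behind mediator, baseline viral suppression and outcome (a = 0.5 SD, ρ = 0.5, log odds 0.5 to 1.0 per SD, all assumed). The spurious share was 35% to 70% with neither covariate and 34% to 65% or slightly less with baseline viral suppression alone. With the baseline mediator alone it was about 0% if that score carries the whole trait and 23% to 47% if the score is a noisy measure of it. The baseline mediator does most of the work.

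**The case against.** Several points against the concern stand.

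- The covariate list is illustrative. A reader might infer that the analysts will leave baseline values out. The text does not say so; it only fails to name them. An open list still lets the model be chosen after the results are seen.
- A reader might infer that both main mediators are affected in A versus B. Section 8.3 expects similar gains in household economic conditions in the two microfinance arms. If that holds, the artefact for that mediator is about zero.
- The hypotheses are worded as improvements, so a change-from-baseline mediator is not ruled out. A change score does not replace adjustment: with ρ = 0.5, M − M0 contains (0.5 − 1)·M0 = −0.5·M0, so it remains related to baseline status, with the sign reversed.
- The 5-point scenario gives larger shares than the planned 15-point effect. Addendum item 10 reports a high overall suppression rate, which makes 85% reasonable, but gives no figure.
- The access instrument is coarse. A single six-month recall question decides whether most later barrier questions are asked, so the baseline score is likely to be noisy.
- Baseline viral load is a record value up to 12 months old, is not drawn if absent (section 6.2), and alone removes little bias.
- The sensitivity analysis addresses this kind of confounding, and the qualitative work gives a second view. The first has no stated method, and neither replaces adjusting for a variable already measured.

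**Conclusion.** The concern holds as a specification gap in section 8.3, mainly for access to care in A versus B. Under the stated assumptions, about 23% to 48% of a 5-point effect could be reported as mediated when none is. The figure is about 20% for a 15-point effect at ρ = 0.5, less with weaker confounding, and about 0% if the intervention does not move the mediator. These figures illustrate a direction and a plausible order of size for suppression; retention was not simulated, and none of them predicts this trial's result.

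Two stronger readings are not supported. One is that the mediation findings will be wrong: that depends on the unknown strength of confounding and on covariates the plan leaves open. The other is that adding the baseline score cures the problem: it gives 0% only when that score is free of error. This is a mechanism aim, and the Aim 1 primary analysis is untouched.

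**What to change.** In section 8.3, require both A versus B models of the difference method (with and without the follow-up mediator) to include, besides the listed covariates:

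1. the baseline score of the mediator being analysed, which is the essential term;
2. log(baseline viral load + 1), for consistency with Aim 1.

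State that missing baseline values are multiply imputed, as addendum item 10 does for Aim 1. Keep the planned sensitivity analysis and give its method and parameter range, since it must deal with what a noisy baseline score leaves behind.

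Confine the baseline-mediator requirement to A versus B. Microfinance members had to be active in a group for six months before enrolment (section 3.3.1), so in comparisons with arm C their baseline score may already reflect microfinance.

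The cost is a few sentences in the plan. No new data or visits are needed; the extra work is imputing some baseline values.

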9.1 Aim 3 procedures

Costs attributable to the intervention will be collected during the randomized controlled trial (Aim 1) for each relevant study period at 6, 12, and 18 months. Costs will be recorded using a cost tracking tool developed specifically for this study. We will estimate differences in the intervention arms (MF+ICB and MF+SOC) and the controls (SOC). The differences in costs among the control and intervention arms will be defined as the incremental costs (Δ C). Cost estimates for the controls will be obtained from

AMPATH's existing electronic medical records (AMRS) as well as accounting and administrative records, and interviews with n=5 key informants such as administrative directors, comptroller, and local managers. In particular, we will use project and administrative records to conduct a cohort-based, microcosting approach. We will assess cost differences between the control and intervention arms including the total costs of the medications (ART, NCD control, etc.), as well as transportation and wait time costs. For each participant, we will review the AMRS to determine the actual utilization of ART, non-ART drugs, laboratory tests used, and clinic visits for each patient.

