9.2 Aim 3 statistical analyses

Costs will be calculated from three distinct perspectives. First, we will take the perspective of AMPATH as a provider of care. Total costs will be defined as the sum of fixed and variable costs. Variable costs for each patient will be calculated by multiplying the number of units of each good or service used by the unit cost. Costs of ART will be obtained from the official AMPATH/PEPFAR supplier in Kenya. Unit costs for non-ARV drugs will be estimated by reviewing invoices and interviewing key informants. Clinical care unit costs will be estimated by multiplying the time of the clinical interaction (based on time motion logs) by the amount spent on staff salaries by level (medical officer, nurse, etc.) and overhead. All costs incurred by the project, not directly attributable to individual participants will be considered as part of the fixed costs. These are usually costs that are exercised regardless of the volume of participants (cleaning, maintenance, utilities, etc.). Fixed costs will also include any equipment bought (new testing machines, motorcycle, rent/space costs, etc.) which will be discounted at a rate of 5% per year to account for depreciation. Total fixed costs will be allocated to all the participants proportionally. Second, we will take into account costs from the patients point of view, which will include time and transport costs to the place where care is received (i.e., the clinic for the SOC vs. the microfinance meeting place for the MF+ICB group). Third, we will perform a potential cost-saving estimation from the point of view of government and donors where financial outlays are compared into the future to gauge the extent to which the proposed intervention can be financially self-sustained.

Effectiveness: We will use the changes in primary and secondary outcomes, as explained in Aim 2; namely: viral suppression and retention-in-care. The incremental effectiveness (ΔE) will be defined as the difference in outcomes between the SOC and the intervention groups.

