Incremental Cost-Effectiveness Ratio (ICER) will be defined as incremental cost over incremental effectiveness ($\Delta C/\Delta E$). In addition, we will model incremental costs per disability-adjusted life year (DALY) averted to make the results comparable to the international cost-effectiveness literature. We will model the effects over the life span using the Sullivan method discounting future effects. For the net benefits estimation, we will transform costs into constant 2018 USD using the Kenyan consumer price index and the international average exchange rate to convert from Kenyan shillings (KES) to USD. We will compare the cost per DALY saved to the Kenyan income per capita (GDPpc) and deem the intervention extremely cost-effective if \$/DALY is less than 1*GDPpc, highly cost-effective if \$/DALY is less than 3*GDPpc.

Sensitivity Analysis: We will use sensitivity analyses to describe the scope and nature of the inherent uncertainties surrounding the cost-effectiveness estimates. Each parameter in the model will be varied across a plausible range of in a series of one-way sensitivity analyses and those that exhibit the largest magnitude of influence either in effects, costs, or the resultant cost-effectiveness ratio, will be varied together in multi-way sensitivity analyses. In addition, we will conduct threshold analysis, whereby we will point out the values at which the intervention options may no longer be cost-effective; we will use a probabilistic uncertainty analysis for the variables that have an underlying probability distribution.

The final cost-effectiveness results will be measured with incremental cost effectiveness ratios comparing the SOC with each of the additional interventions. In addition, given that each of the innovations may have an optimal level of scale and diffusion, and potential cost savings from the perspective of each of the actors. To estimate return on investment we will use a cost-utility approach that we have successfully used for HIV testing and can be adopted for HIV treatment retention interventions.

10. Protection of human subjects

This study involves research that is classified as non-exempt human subjects research. All procedures of this research will be conducted in accordance with 45 CFR Part 46 and will be approved by the Moi University School of Medicine IRB (the IRB of record) and the Brown University Institutional Review Board (the prime award recipient).

10.1Risks to human subjects

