and capital (e.g., fuel) resources needed to travel to the distinct health facilities to ascertain secondary outcome data for each matched patient were prohibitively high.

- 8. In order to enroll 300 patients receiving standard facility-based care and not engaged in a microfinance group (SOC), the original protocol stated that enrolled microfinance group participants should be matched 3:1 to eligible SOC patients on county, gender, age (+/- 5 years), and health facility. The matching protocol was revised on February 8, 2022 such enrolled microfinance group participants were matched 3:1 to eligible SOC patients on gender and age (+/- 5 years of microfinance participant). This change was made because most SOC patients who were invited to enroll in Busia County after February 8, 2022 were ineligible for study participation due to membership in either a microfinance group or a community ART Group. This change resulted in approximately 90 enrolled microfinance group members in Busia County being matched to 30 SOC patients in Trans Nzoia County on (1) age (within +/- 5 years of the GISHE participant's age) and (2) gender.
- 9. The original project protocol stated that group randomization would occur using a computer-generated sequence to randomize microfinance groups to receive either integrated community-based care (ICB) or standard of care, and that the randomization process would be conducted centrally by biostatisticians at Brown University.

The cluster randomization approach was revised to use a transparent, community-engaged approach to increase transparency and cultivate trust between research personnel and study participants, clinical personnel, and local community leaders. Below is a summary of the steps that were implemented for at each community-engaged randomization ceremony. Six randomization ceremonies were conducted among the 57 microfinance groups following enrollment:

- 2 randomization ceremonies each with 10 microfinance groups were conducted in Phase I groups
- 2 randomization ceremonies each with 11 and 8 microfinance groups were conducted in Phase II groups
- 1 randomization ceremony with 15 microfinance groups was conducted in Phase III groups
- 1 randomization ceremony with 3 microfinance groups was conducted in Phase IV groups

The below steps describe the community-engaged randomization process.

Participants

- 1. Group leaders (Chairperson, Secretary & Treasurer)
- 2. AMPATHPlus Senior Technical Officers (STO)

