Stability analysis: We performed stability analysis to determine how sensitive the results were to different specifications of the model used in the implementation of the doubly robust generalized estimating equation. This was done by modeling continuous covariates using second order polynomials and including interactions between the covariates. The results were similar to what is presented in the main manuscript.

Analysis plan for secondary objectives: The analyses of both secondary objectives were conducted using a doubly robust generalized estimating equation with a logit link function accounting for potentially differential dropout and confounding⁸. The generalized estimating equation models included the intervention arm, used an independence working correlation matrix and the variance was estimated using a sandwich variance estimator for clustered data. The intervention effects were estimated using the log odds ratio coefficient of intervention in the generalized estimating equation. The primary hypothesis tests of the intervention effects were conducted using a Wald test and 95% Wald-based confidence intervals were calculated.

Handling of confounding and dropout: Implementation of the method relies on specifying a model for the dropout probability and two outcome models (one for each treatment arm) and these procedures account for both dropout and confounding (under the assumption of no unmeasured confounding and a non-informative dropout). All three models were logistic regression models with linear main effects of county, log(viral load at baseline+1)), schooling achieved, age, and gender and the model for dropout probability also included the treatment arm.

Handling of missing data: Multiple imputation was used to account for missing data on baseline covariates and Rubin's rule for variance estimation was used for variance estimation.

Rational for revisions to original analysis plan:

We modified the primary outcome definition without looking at the data and to be in compliance with national guidelines that changed during the study's follow-up period. As a sensitivity analysis we reran the analysis with the current definition of viral suppression (i.e., <200 copies/mL) used for all participants, and the results were very similar to what the primary analysis shows.

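### Aim 3 names no confounding adjustment for the cost or effect differences against the non-randomised SOC arm, and does not say which effect estimate enters the ICER.

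*Combined protocol and SAP*

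**What the plan says.** All references are to the combined protocol and SAP.

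- **Numerator (section 9.1).** "The differences in costs among the control and intervention arms will be defined as the incremental costs". The control is SOC. No covariates, weights or standardisation are named.
- **Denominator (section 9.2).** Incremental effectiveness "will be defined as the difference in outcomes between the SOC and the intervention groups". The outcomes are introduced thus: "We will use the changes in primary and secondary outcomes, as explained in Aim 2; namely: viral suppression and retention-in-care".
- **Ratio (section 9.2).** "The final cost-effectiveness results will be measured with incremental cost effectiveness ratios comparing the SOC with each of the additional interventions". The opening of section 9 also hypothesises about MF+ICB against MF+SOC, but that randomised pair does not appear in this sentence.
- **Sensitivity analyses (section 9.2).** One-way, multi-way, threshold and probabilistic analyses of model parameters.
- **Same contrasts in Aim 1 (Addendum item 10, secondary objectives).** A doubly robust GEE with county, log baseline viral load, schooling, age and gender. The text says "these procedures account for both dropout and confounding", assuming no unmeasured confounding. The effect is a log odds ratio.
- **Matching (section 4.2, revised by Addendum item 8).** County, age within 5 years, gender and facility at first; from 8 February 2022, gender and age only. Item 8 reports "approximately 90 enrolled microfinance group members in Busia County being matched to 30 SOC patients in Trans Nzoia County".

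The Addendum does not revise Aim 3.

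**The concern.** An ICER against SOC needs two causal differences: what microfinance or integrated care adds in cost, and what it adds in effect. People in savings groups may differ from clinic patients who are not in such groups in ways that drive both. The trial accepts this for viral suppression, since Addendum item 10 adjusts these contrasts for five covariates. Aim 3 carries none of that over to cost, nor explicitly to effect.

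If the definitions are followed as written, any imbalance in baseline viral load, schooling, county or facility is counted as part of the cost or benefit of the programme. The cost per suppressed or retained patient would inherit that error. Place matters for cost in particular, because section 9.1 includes transport and waiting time. Varying parameters over plausible ranges does not reveal this: a confounded increment stays confounded at every parameter value.

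**Working it through.** No cost, cost variance or ICER is stated, so there is no figure of the plan's own to reproduce. The check compares texts, with three short calculations.

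**1. What matching covers, against what Aim 1 adjusts for**

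| Factor | Matched to 8 Feb 2022 | Matched after | Adjusted in Addendum item 10 |
|---|---|---|---|
| Age | yes | yes | yes |
| Gender | yes | yes | yes |
| County | yes | no | yes |
| Facility | yes | no | no |
| Baseline viral load | no | no | yes |
| Schooling | no | no | yes |

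Shares affected by cross-county matching, on planned numbers: 90/900 = 10% of microfinance members and 30/300 = 10% of SOC patients. Addendum item 7 adds that many matched SOC patients attended facilities other than those used by most microfinance members.

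**2. Which effect enters the denominator**

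- *Section 9.2 alone:* a difference from SOC with no adjustment named. Numerator and denominator then have the same form, and both are unadjusted.
- *The Aim 1 estimate from item 10:* adjusted, but nothing in Aim 3 points to it.
- *The cross-reference to Aim 2:* section 8.3 describes mediation models adjusted for education, location, gender and age. They are built to split an effect into pathways, and the text does not say that they supply the total difference against SOC.

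For retention, Addendum item 11 redefines the outcome as binary but describes no analysis against SOC with the item 10 covariates.

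**3. A log odds ratio is not a difference**

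With SOC suppression p0 and odds ratio OR, p1 = OR × p0 / (1 − p0 + OR × p0), and the risk difference is p1 − p0. For an assumed OR of 1.5:

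| Assumed p0 | p1 | Risk difference |
|---|---|---|
| 0.20 | 0.30/1.10 = 0.273 | 0.073 |
| 0.50 | 0.75/1.25 = 0.600 | 0.100 |
| 0.90 | 1.35/1.45 = 0.931 | 0.031 |
| 0.95 | 1.425/1.475 = 0.966 | 0.016 |

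The same OR gives differences from 0.016 to 0.100, so the plan must say how it would be converted. Addendum item 10 reports a high overall suppression rate, which points to the lower rows.

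**4. How an error passes into the ratio (illustrative inputs only)**

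An error e in the cost increment ΔC multiplies the ICER by 1 + e/ΔC, whatever the effect. With ΔC = 50 and e = ±10, that is ±20%: at an effect of 0.05 the ICER moves from 1,000 to 800 or 1,200. An error in the effect acts through the denominator: with ΔC = 50, an effect of 0.03 in place of 0.05 moves the ICER from 50/0.05 = 1,000 to 50/0.03 = 1,667. These inputs are assumed; only the proportions carry over.

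**The case against.** **Silence is not a commitment to a crude analysis.** Sections 9.1 and 9.2 define quantities, not estimators. This is fair, but an analyst who follows them has no instruction to adjust, whereas Aim 1 gives that instruction in detail for the same arms.

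**Arm C is matched.** Age and gender were matched throughout, county and facility for the earlier part, and section 3.4.1 announces a wider aim of matching on covariates tied to microfinance enrolment and suppression. This stands in part: confounding is a risk, not a demonstrated fact, and age and gender are weak candidates for it. But the operative list in section 4.2 has four factors, two were later dropped, and the trial still adjusts for baseline viral load and schooling.

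**Place-based costs belong to one perspective.** Section 9.2 puts patient time and transport in the second of three perspectives, and fixed costs are spread proportionally over participants. So the transport argument does not reach every ICER. Utilisation of drugs, tests and visits could still differ with unmatched factors.

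**A stronger reading.** A reader might infer that every planned ICER divides an unadjusted cost by an adjusted effect, so that the two parts do not match. The documents do not support that. Section 9.2 gives the effect the same form as the cost. A mismatch arises only if the adjusted suppression effect is paired with an unadjusted cost difference, which the plan neither states nor rules out. It could not be shown for retention, where no effect adjusted for the item 10 covariates is described.

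**Conclusion.** The concern holds as a gap in Aim 3. Cost and effect differences against a non-randomised arm are defined without any adjustment, SOC is the reference for all the final ICERs, and the source and scale of the effect estimate are left open. The trial's own Aim 1 analysis shows that it regards adjustment of these contrasts as necessary.

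Neither the size nor the direction of the bias can be computed from the documents. What they do show is that two of the five covariates used in Aim 1 were never matched, and that county was not matched for about 10% of planned SOC patients. Nothing shows that a conclusion against the GDP-per-capita thresholds in section 9.2 would change. The point concerns only contrasts with SOC; a comparison of the two randomised arms would not carry this problem. Because the remedy is cheap and uses a covariate set that the trial has already chosen, the change should be made.

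**What to change.** Add to section 9.2:

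1. Estimate the cost difference and the effect difference against SOC with the Addendum item 10 covariates: county, log baseline viral load, schooling, age and gender. Do this for suppression and for the revised binary retention outcome.
2. Standardise both to one stated target population and report both on the absolute scale (mean cost difference, risk difference). This also settles the conversion from a log odds ratio.
3. Handle missing data as suits each outcome. Utilisation comes from medical records, so cost need not share the dropout weights built for the 18-month viral load.
4. Form the ICER from these two differences. Take its interval from a joint bootstrap that resamples whole microfinance groups in Arms A and B and individuals in SOC, recomputing both differences each time.
5. Replace the cross-reference to Aim 2 with a statement of which estimate is the denominator.

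The cost model (linear or gamma) can be left to the sponsor. The covariates are already used in Aim 1, and section 9.1 plans a record review of utilisation for each participant. Patient travel and waiting costs need a check: the survey as shown in Appendix III records transport difficulty but no amounts, and the cost tracking tool is not shown.

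The price is a revised paragraph, modest programming and some dependence on the cost model. Because the Addendum reports the Aim 1 analysis as done, the change should be dated and described as made after it.
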